Briefly, patients will undergo baseline eligibility screening within 2 weeks prior to enrollment, including a medical history, physical examination, and assessment of performance status and hematology and chemistry parameters. Baseline assessment of disease status will be based on results of a bone marrow aspirate and biopsy for patients with AML and MDS, and a CT/PET scan (with a bone marrow exam for history of disease involvement) for patients with lymphoma. Baseline and subsequent bone marrow and peripheral blood samples will be obtained for correlative assays. Disease response assessment (bone marrow aspirate and biopsy and/or CT/PET) will be performed at baseline, and then every 3 months for 2 years, as well as any time if relapse is suspected. Specific procedures to be performed during the trial, as well as their prescribed times and associated visit windows, are outlined in the trial flow chart – Section 7.0. Details of each procedure are provided in Section 8.0 – trial procedures. After 24 months, ongoing disease re-assessments will be performed at the discretion of the treating physician. Any patient who experiences biopsy-proven disease progression at any time will be removed from study, and alternative treatment can be recommended at the treating physician's discretion. Subjects are not eligible for re-treatment on with pembrolizumab in the setting of this protocol should they experience a disease relapse after completing 24 months of therapy. After the end of treatment, each subject will be followed for 30 days for adverse event monitoring (serious adverse events will be collected for 90 days after the end of treatment). Subjects who discontinue treatment for reasons other than disease progression will have post-treatment follow-up for disease status until disease progression, initiating a non-study cancer treatment, withdrawal of consent, or becoming lost to follow-up. All subjects will be followed by telephone contact for overall survival until death, withdrawal of consent or the end of the study, whichever comes first.

The primary objective of this trial is to determine whether administration of pembrolizumab is tolerable in patients who have experienced disease relapse following alloSCT. Secondary objectives include analysis of efficacy parameters (ORR, DOR, OS). Correlative studies to examine the effect of PD-1 blockade therapy on T cell parameters and clonality, as well as on donor chimerism are planned as exploratory analyses.

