A DLT is defined as the development of grade 3 or 4 acute GVHD (defined by the Gluckensberg scale), graft rejection, the development of any unexpected grade > 2 toxicity felt to be related to pembrolizumab, or the development of > grade 2 dysfunction of a vital organ felt to be secondary to an immune-related adverse event within 90 days following the initiation of pembrolizumab treatment. For immune-related adverse events that do not meet criteria for a DLT, but do meet criteria for a treatment-limiting toxicity (TLT), for example grade 2 acute GVHD, pembrolizumab will be held until the toxicity has

decreased to \leq grade 1. It will be permanently discontinued if delayed for >12 weeks. For patients who develop GVHD or an immune-related adverse event while on pembrolizumab, corticosteroid therapy and potentially other immunomodulatory agents will be initiated.

If the safety and feasibility of pembrolizumab is confirmed in this patient cohort, a phase II expansion cohort may be considered, particularly for disease subtypes where objective responses have been observed.

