irAEs are defined as an adverse event associated with pembrolizumab exposure and mediated through an immune mechanism. irAEs may be predicted based on the nature of the known mechanism of action of pembrolizumab, as well as experience with other immunotherapies with a similar mechanism of action. Special attention should be paid to AEs that are suggestive of potential irAEs. An irAE can occur shortly after the first dose, or several months after the final dose of pembrolizumab. If an irAE is suspected, effort should be made to rule out other potential etiologic causes prior to labeling an AE as an irAE. Information on how to identify and evaluate irAEs is included in the event of clinical interest and immune-related adverse event guidance document located in the administrative binder.

Events of clinical interest (ECI)

ECIs are non-serious and serious AEs that may or may not be irAEs. ECIs must be reported to Merck within 24 hours regardless of attribution to pembrolizumab.

Information on how to identify and report ECIs can be referenced in Section 8.2.3.2.

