8.1.6.3 SAFETY FOLLOW-UP VISIT

The mandatory safety follow-up visit should be conducted approximately 30 days after the last dose of pembrolizumab treatment or before the initiation of a new anti-cancer treatment, whichever comes first. The safety follow-up visit can be done on the same day as the end of study visit (Section 8.1.6.2) or the end of treatment visit (Section 8.1.6.1). All AEs that occur prior to the safety follow-up visit should be recorded. Subjects with an AE of grade > 1 will be followed until the resolution of the AE to grade 0-1, or until the beginning of a new anti-cancer therapy, whichever occurs first. SAEs that occur within 90 days of the end of treatment or before initiation of a new anti-cancer treatment should also be followed and recorded.

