8.2.3 IMMEDIATE REPORTING OF ADVERSE EVENTS

8.2.3.1 SERIOUS ADVERSE EVENTS

A serious adverse event is any adverse event occurring at any dose or during any use of pembrolizumab that:

- Results in death;
- Is life threatening;
- Results in persistent or significant disability/incapacity;
- Results in or prolongs an existing inpatient hospitalization;
- Is a congenital anomaly/birth defect;
- Is a new cancer (that is not a condition of the study);
- Is associated with an overdose;
- Is another important medical event

Refer to **Table 11** for additional details regarding each of the above criteria.

Progression of the cancer under study is not considered an adverse event unless it results in hospitalization or death.

Any serious adverse event, or follow up to a serious adverse event, including death due to any cause other than progression of the cancer under study (reference Section 7.2.3.3 for additional details) that occurs to any subject from the time the consent is signed through 90 days following cessation of treatment, or 30 days following cessation of treatment if the subject initiates new anticancer therapy, whichever is earlier, whether or not related to pembrolizumab, must be reported within 24 hours to the principal investigator and Merck either by electronic media or paper.

Additionally, any serious adverse event, considered by an investigator who is a qualified physician to be related to pembrolizumab that is brought to the attention of the investigator at any time outside of the time period specified in the previous paragraph also must be reported immediately to the principal investigator and Merck.

All subjects with serious adverse events must be followed up for outcome.

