9.1.1 SAFETY ANALYSES

The study will initially enroll 12 patients in the first stage of the two-stage trial design. The accrual rate will be 1 patient/month in relapsed/refractory myeloid and B cell malignancies following allogeneic stem cell transplant to assess the safety and feasibility of pembrolizumab. If at least 5 of the first 12 patients complete pembrolizumab treatment without developing a DLT, we will open an expansion cohort to enroll with plans to enroll 14 additional patients should DLT-associated stopping rule not be met in the first 12 patients. Specifically, if 5 or more of the first 12 enrolled patients develop a DLT, including grade 3-4 GHVD, then the study will be halted. If at least 14 of the 26 patients remain DLT-free, we would have sufficient evidence to warrant further study of pembrolizumab in a future trial. Furthermore, if severe GVHD (grade 3-4) develops within the first 90 days of pembrolizumab treatment in each of the first 5 patients treated on the study (i.e. develop a DLT), it will be permanently closed to accrual as a measure to ensure safety.

Toxicity will be graded per the CTCAE guidelines and the maximally tolerated dose will be defined a less or equal than 1 in 6 patients with DLTs. All patients who receive any amount of the study drug will be evaluable for toxicity.

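### The collection rules do not guarantee that DLTs are ascertained to day 90 in patients who receive three or fewer doses or switch early to new therapy, and the plan does not say how such patients are counted

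*Combined protocol and SAP*

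**What the plan says.** Section 2.1 defines a DLT as grade 3-4 acute GVHD, graft rejection, unexpected related toxicity above grade 2, or immune-related vital-organ dysfunction above grade 2, "within 90 days following the initiation of pembrolizumab treatment". Section 9.1.1 makes everyone who is dosed evaluable: "All patients who receive any amount of the study drug will be evaluable for toxicity".

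The collection rules are these:
- **All adverse events.** Section 2.1 sets two periods, both counted from when treatment stops: "each subject will be followed for 30 days for adverse event monitoring (serious adverse events will be collected for 90 days". Section 8.1.6.3 places the safety visit about 30 days after the last dose, or before new anticancer treatment if that is sooner, and adds: "All AEs that occur prior to the safety follow-up visit should be recorded".
- **Serious events.** Section 8.2.3.1 requires reporting for 90 days after cessation, "or 30 days following cessation of treatment if the subject initiates new anticancer therapy, whichever is earlier". Section 8.1.6.3 words the cut-off as the start of new treatment. Related serious events that reach the investigator later are still reportable.
- **Events of clinical interest.** Section 8.2.3.2 runs to 90 days after cessation, or 30 days after new therapy begins.
- **After progression.** Section 2.1: "Any patient who experiences biopsy-proven disease progression at any time will be removed from study". Section 6.8 allows continued monitoring. Section 8.1.6.4.1 provides a 12-weekly telephone call for survival status.
- **Chimerism.** The flow chart schedules it before treatment, at week 13 and every 12 weeks thereafter, and in the Post-Treatment column. It is not ticked at End of Treatment (section 7.6) and is not in the section 8.1.6.1 list.

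On counting, section 9.2.4.1 and the final rule (14 of 26) refer to patients who stay free of DLT. The halt rule in 9.1.1 and 9.1.3 counts patients who develop one. The stage 1 rule in 8.2 and 9.1.1 instead asks that at least 5 of 12 complete treatment without one.

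**The concern.** Tolerability is the primary objective and is decided on 12 and then 26 patients, so one or two misclassified patients can change the decision. A patient who has one or two doses, progresses and moves to other treatment can leave event collection well before day 90. Under the rules that count DLTs, an event nobody recorded cannot count against the drug. Section 6.6.1.1 itself warns: "An irAE can occur shortly after the first dose, or several months after the final dose of pembrolizumab". Section 4.1 describes a very poor prognosis for aggressive disease relapsing after transplant, so early exits are plausible, although the documents give no rate.

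No section sets a minimum observation time for a DLT-free classification, a replacement rule, or a classification for a patient who leaves before day 90 without a recorded DLT.

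**Working it through.** **1. Where the gap lies.** Dosing is every 21 days (Table 1), so doses fall on days 1, 22, 43, 64 and 85. Adding 30 days for all events and 90 days for serious events gives:

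| Last dose (day) | All-event recording ends | Serious-event collection ends, no new therapy |
|---|---|---|
| 1 | 31 | 91 |
| 22 | 52 | 112 |
| 43 | 73 | 133 |
| 64 | 94 | 154 |

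Without new therapy, only patients with three or fewer doses fall short of day 90, and only for non-serious events. With new therapy, general recording ends before it starts, and section 8.2.3.1 cuts serious-event reporting to 30 days after cessation. Progression first found at the scheduled week 13 assessment (about day 85) does not create the gap.

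**2. Graft rejection.** A patient who progresses or starts new therapy before week 13 misses the week 13 chimerism sample, has none ticked at End of Treatment, and then moves to survival calls. No test after the pre-treatment sample is scheduled for that patient.

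**3. The plan's own design figures.** Section 9.2.4.1 gives p0 = 0.40, p1 = 0.65, alpha 0.05, power 80%, at least 5/12 and then at least 14/26 DLT-free. The pass probability at rate p is the sum over x from 5 to 12 of P(X1 = x) × P(X2 ≥ 14 − x), with X1 ~ Bin(12, p) and X2 ~ Bin(14, p). This gives 0.104 at p = 0.40 and 0.907 at p = 0.65, so the stated error rates are not reproduced. A minimax search does return n1 = 12 and N = 26, but with cut-offs of 6 and 15 (0.047 and 0.809). That is a separate matter; here 0.104 is simply the baseline. If the halt at 5 or more DLTs in 12 governs, at least 8 of 12 must be DLT-free, and the baseline is 0.033.

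**4. Effect if early leavers are scored DLT-free.** Assumptions: true 90-day DLT-free rate 0.40; constant hazard; exit unrelated to DLT risk; a share f leaves observation at day t; a share s of their later DLTs is still caught through serious-event or clinical-interest reporting.
- DLT risk by day t: E = 1 − 0.4^(t/90), which is 0.271 at day 31 and 0.411 at day 52.
- Apparent DLT-free rate: 0.4(1 − f) + f[1 − E − s(0.6 − E)].
- Example, t = 52, f = 0.2, s = 0: 0.32 + 0.2 × 0.589 = 0.438.

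| Exit day, share | Later DLTs caught | Apparent rate | False pass, printed cut-offs (baseline 0.104) | False pass with halt (baseline 0.033) |
|---|---|---|---|---|
| 52, 20% | 80% | 0.408 | 0.119 | 0.038 |
| 52, 20% | 50% | 0.419 | 0.144 | 0.048 |
| 52, 20% | 0% | 0.438 | 0.194 | 0.066 |
| 31, 30% | 80% | 0.420 | 0.146 | 0.048 |
| 31, 30% | 50% | 0.449 | 0.228 | 0.080 |
| 31, 30% | 0% | 0.499 | 0.405 | 0.161 |

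**5. Effect if early stoppers are scored as failures at both stages.** At a true rate of 0.65 the success rate becomes 0.65(1 − f), which is 0.585, 0.520 and 0.455 for f = 10%, 20% and 30%. Power falls from 0.907 to 0.739, 0.490 and 0.246. For an unsafe drug with f = 20%, the rate is 0.40 × 0.8 = 0.32 and the pass probability falls from 0.104 to 0.016.

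**The case against.** The strongest reply is that the plan already collects serious events for 90 days after treatment, which spans the DLT window from any last dose, and that most grade 3-4 GVHD would probably be serious. Clinical-interest reporting can outlast new therapy by 30 days, and section 5.3 places grade 2 or higher immune-related events in that class. Sections 8.1.4.1 and 8.1.6.1 press for continued follow-up after stopping, and section 7.6 ticks event review at post-treatment visits. This stands: a reader might infer that serious DLTs are generally lost after day 31, and without new therapy the documents do not support that. It does not close the gap. DLTs above grade 2 need not be serious, the numbered list in 8.2.3.2 names neither acute GVHD nor graft rejection (the separate guidance document may widen it), and a switch to new therapy shortens serious-event reporting.

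A reader might also infer that the plan expressly scores early leavers as DLT-free. It does not. That is the natural reading of the halt and final rules, but the stage 1 wording about completing treatment points the other way.

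Nor is it right that no early leaver is tested for graft loss. Patients who stop for reasons other than progression enter follow-up, where chimerism is ticked, and the section 7.6 footnote allows the safety visit to coincide with a post-treatment visit. The point holds for those who progress or start new therapy before week 13.

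Finally, ending collection at new therapy has a rationale: section 4.4 cites acute GVHD in up to 40-60% after DLI, so later events are hard to attribute. That argues for showing such events separately rather than leaving them uncollected.

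**Conclusion.** The concern holds in this limited form. For patients with three or fewer doses or an early switch to new therapy, following the plan as written can miss non-serious DLT-grade events, DLTs after the switch and, in those who progress or switch before week 13, graft rejection. Their place in the primary count is undefined.

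If they are scored DLT-free, the false-tolerable probability rises from 0.104 to 0.119-0.194 (20% leaving at day 52) or 0.146-0.405 (30% leaving at day 31). With the 5-DLT halt it rises from 0.033 to 0.038-0.066 or 0.048-0.161. The upper ends assume that no later DLT is caught and are bounds, not expectations. If early stoppers are failures, the bias reverses and power drops.

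The exit share, exit day, capture share and constant hazard are assumptions; the documents give none of them, nor do they say that early exits are mainly due to progression. I take the 90 days to apply to every DLT component. If section 9.2.4.1's end-of-treatment time point governs instead, early leavers are observed for even less time.

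**What to change.** - In 8.1.6.3, 8.2.3.1 and 9.1.1, state that the DLT components (acute GVHD grade, graft status, related toxicity above grade 2, organ dysfunction) are recorded for every treated patient through day 90 from first dose, whatever the progression, discontinuation or new-therapy status. Use chart review and the existing telephone contact, made at about day 90 with a short structured question set.
- In 8.2, 9.1.1, 9.1.3 and 9.2.4.1, reconcile completing treatment without a DLT with remaining DLT-free, and say how a patient not observed to day 90 is counted.
- At 12 and at 26 patients, report how many DLT-free patients were observed to day 90, and show DLT counts with and without events after new therapy.
- Optionally, add chimerism to the End of Treatment blood draw.

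The cost is protocol wording, one timed contact and perhaps one blood tube, with no added patients. The alternative of replacing patients with incomplete windows would need 26/(1 − f) enrolled: 29, 33 or 38 at 10%, 20% or 30% early exit. The drawback of the preferred fix is that events after new therapy are harder to attribute, hence the two displays.

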9.1.2 EFFICACY ANALYSES

The intention-to-treat population, defined as subjects who received at least one dose of pembrolizumab, will serve as the primary analysis population in this study. The primary efficacy endpoint is the overall response rate (ORR), defined as those patients who achieve a PR or CR (lymphoma), PR or CR (MDS), or a CR, CRp, CRi or PR (AML). Secondary efficacy endpoints include duration of response (DOR) and overall survival (OS).

An outline of the efficacy analysis strategy is shown in Table 12 below.

Table 12. Primary analysis strategy for efficacy endpoints

Endpoint/Variable (Description, Time Point)	Statistical Method	Analysis Population	Missing Data Approach
Primary:			
Overall response rate (ORR) using defined criteria	Exact test of binomial parameter	ITT	Subjects with missing data are considered non-responders
Secondary:			
Duration of response (DOR)	Summary statistics using Kaplan-Meier method	All responders	Non-responders are excluded in analysis
Overall survival (OS)	Summary statistics using Kaplan-Meier method	ITT	Censored at last assessment

9.1.3 INTERIM ANALYSIS

After the first 12 patients have been enrolled and have received at least 1 dose of pembrolizumab, an interim safety analysis will be performed. If < 5 of the first 12 patients develop a DLT (including grade 3-4 acute GVHD) following pembrolizumab treatment, an expansion cohort of 14 additional patients will be enrolled in order to obtain a more robust safety signal, as well as to enhance numbers of treated patients for efficacy analyses, given that patients with a wide variety of hematological malignancies will be enrolled. However, if ≥ 5 of the first 12 enrolled patients develop a DLT, then the study will be permanently closed to accrual. Furthermore, if severe GVHD (grade 3-4) develops in each of the first 5 patients treated on the study, it will be permanently closed to accrual as a measure to ensure safety.

9.2 STATISTICAL ANALYSIS PLAN

9.2.1 HYPOTHESES

The objectives and hypotheses of the study are stated in Section 3.

9.2.2 ANALYSIS ENDPOINTS

9.2.2.1 SAFETY ENDPOINTS

Safety measurements are described in Section 8.

9.2.2.2 EFFICACY ENDPOINTS

Efficacy endpoints that will be evaluated for are listed below.

The primary efficacy endpoint is the overall response rate (ORR), defined as the proportion of subjects in the analysis population who achieve at least a partial response to pembrolizumab. Specifically, for B cell lymphoma patients, partial and complete responses will be defined according to the International Working Group criteria³⁹ (Appendix). For MDS patients, partial and complete responses (including cytogenetic responses) will be defined according to the International Working Group criteria⁴⁰. Lastly, for AML patients, complete (including CR, CRp, CRi), and partial responses will be defined according to the European Leukemia Net response criteria (Appendix)⁴¹.

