9.0 STATISTICAL ANALYSIS PLAN

9.1 STATISTICAL ANALYSIS PLAN SUMMARY

This section contains a brief summary of the statistical analysis for this trial. Full details can be found in the statistical analysis plan (SAP) in Section 8.2.

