12.6 IDENTIFICATION AND FOLLOW-UP OF LESIONS IN AML

12.6.1 COMPLETE REMISSION (CR)

For subjects to be classified as being in CR, they must have bone marrow regenerating normal hematopoietic cells and achieve a morphologic leukemia-free state ($< 5\%$ bone marrow blasts in bone marrow, no blasts with Auer rods and no persistence of extramedullary disease) and must have an ANC $\geq 1 \times 10^9/\text{L}$ and platelet count $> 100 \times 10^9/\text{L}$

and they will be RBC and platelet transfusion independent (defined as 4 weeks without RBC transfusions and 1 week without platelet transfusion).

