12.6.3 COMPLETE REMISSION WITH INCOMPLETE HEMATOLOGICAL RECOVERY (CRI)

For subjects to be classified as being in CRi, they must fulfill all the criteria for CR except for incomplete hematological recovery with residual neutropenia $<1 \times 10^9/L$ and/or platelet count $>100 \times 10^9/L$. RBC and platelet transfusion independence is not required.

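### The ORR responder rules conflict in current text: the AML CRi platelet limit (carried into PR), the status of cytogenetic-only MDS responses, and who reads response

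*Combined protocol and SAP*

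**What the plan says.** **Responder lists.** Section 9.1.2 gives ORR as "defined as those patients who achieve a PR or CR (lymphoma), PR or CR (MDS), or a CR, CRp, CRi or PR (AML". Section 9.2.2.2, the fuller text, adds for MDS: "For MDS patients, partial and complete responses (including cytogenetic responses) will be defined according to the International Working Group criteria". Section 9.1 describes itself this way: "This section contains a brief summary of the statistical analysis for this trial". Table 12 restricts DOR to responders: "Non-responders are excluded in analysis".

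**AML definitions (Appendix 12.6).**
- CR (12.6.1) needs <5% marrow blasts, ANC at least 1 x 10^9/L, platelets above 100 x 10^9/L and transfusion independence.
- CRp (12.6.2) is CR with platelets below 100.
- For CRi (12.6.3), "they must fulfill all the criteria for CR except for incomplete hematological recovery with residual neutropenia" below 1, "and/or platelet count $>100 \times 10^9"/L. It adds: "RBC and platelet transfusion independence is not required".
- PR (12.6.4) must meet CRi, with only the blast rule relaxed.

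**MDS definitions (Appendix 12.5).** CR (12.5.1) and PR (12.5.2) are built on marrow, blood counts and dysplasia. Cytogenetic response has its own heading (12.5.8).

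**Reader.** Section 3.2 has CR or PR determined by an IRC, and 12.6.6 sends response and progression data in all four diseases to IRC review. Sections 8.1.2.6.2, 8.1.2.6.4 and 8.1.2.6.5 provide for local reading and say there will be no central radiology or pathology review.

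**The concern.** A single-arm response rate means only what its responder definition means, and here the definition gives different answers depending on the section consulted.

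- **AML.** The platelet value printed as incomplete recovery in CRi is the one CR requires and the opposite of CRp. Because PR is built on CRi, a patient with a qualifying marrow fall, recovered neutrophils and low platelets is a non-responder as printed.
- **MDS.** A patient whose only response is cytogenetic may or may not count.
- **Reader.** It is unclear whose assessment enters the analysis.

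ORR is the primary efficacy endpoint, although a secondary objective of the trial. Because DOR is analysed in responders only, the same conflicts decide who enters that analysis. The DLT-free endpoint and the two-stage decision do not use response.

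**Working it through.** The documents give no sample size, power or significance level for ORR, so there is no stated figure to reproduce. The check sets the definitions side by side and, for AML, enumerates them.

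**1. AML.** Four two-way factors define a profile: marrow (<5% blasts, or PR range), ANC (≥1 or <1), platelets (>100 or <100), and transfusion independent (TI) or not. That gives 2 x 2 x 2 x 2 = 16 profiles, 8 per marrow class.

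Fixed rules: CR = <5% blasts, ANC ≥1, platelets >100, TI. CRp = the same with platelets <100. Let K be the CRi count rule. Then CRi = <5% blasts and K, with TI not needed, and PR = PR marrow and K. A responder is anyone in CR, CRp, CRi or PR.

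The list in 12.6.3 can be read in three ways. Each is applied with the same logic before and after the sign is changed. Responder counts are <5% marrow + PR marrow.

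| Reading of 12.6.3 | K as printed | K with sign corrected | Printed | Corrected | Gains | Losses |
|---|---|---|---|---|---|---|
| Free-standing test | ANC <1 or plt >100 | ANC <1 or plt <100 | 7 + 6 = 13 | 7 + 6 = 13 | 3 | 3 |
| Exceptions to CR, as waivers | plt >100, any ANC | any counts | 5 + 4 = 9 | 8 + 8 = 16 | 7 | 0 |
| Exceptions to CR, some incompleteness required | ANC <1 and plt >100 | ANC <1 or plt <100 | 4 + 2 = 6 | 7 + 6 = 13 | 7 | 0 |

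- Gains on every reading (3): <5% blasts, ANC ≥1, platelets <100, not TI; and PR marrow with the same counts, TI or not.
- Further gains on the two exception readings (4): ANC <1 and platelets <100, either marrow, TI or not. 3 + 4 = 7.
- Losses on the free-standing reading (3): <5% blasts, ANC ≥1, platelets >100, not TI; and PR marrow with the same counts, TI or not. On the third reading these three are non-responders both before and after. On the waiver reading they are responders throughout.

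So changing the sign alone leaves PR marrows with fully recovered counts outside PR on two of the three readings. Section 12.6.4 has to be handled with 12.6.3.

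**2. MDS.** Section 9.1.2 lists PR or CR. Section 9.2.2.2 has the same list plus the cytogenetic parenthesis, which can mean an added category or a component of CR and PR. Sections 12.5.1 and 12.5.2 contain no karyotype item, so the appendix does not support the second meaning. The partial cytogenetic response in 12.5.8.2 is expressed as a reduction in hematologic improvement, not in abnormal metaphases, and cannot be applied as printed.

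**3. Reader.** Sections 3.2 and 12.6.6 name an IRC; the three Section 8 passages rule out central review. Section 5.4 defines ORR as a proportion but refers back to 3.2 for what an objective response is. Section 3.2 words ORR as an interval, from first response to progression or death.

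**4. Scale.** One reclassified patient moves ORR by 1/26 = 3.8 percentage points, or 1/12 = 8.3 points if the trial stops at 12. Table 12 names an exact binomial test and 9.2.4.2.1 gives 10% as the reference. With X ~ Binomial(26, 0.10): P(X ≥ 5) = 0.112, P(X ≥ 6) = 0.040, P(X ≥ 7) = 0.012.

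**The case against.** **The AML sign is an obvious slip.** Probably so: 12.6.1 and 12.6.2 make the intended direction clear, and a PDF conversion error cannot be excluded. CR, CRp and CRi all count as responses, so confusion among those three labels does not by itself change ORR. Section 8.1.2.6.1 also makes the European LeukemiaNet guidelines the primary means of assessment. What remains is that 9.2.2.2 points to both the Appendix and the cited criteria for AML without ranking them, and that PR and patients without transfusion independence are affected.

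**The fuller text governs MDS.** Section 9.1 is a summary, so 9.2.2.2 should prevail, and the cited criteria may explain the parenthesis. That settles which section to read, not what its parenthesis means.

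**Local reading is for eligibility and management only.** Section 8 does tie local reading to those purposes, and IRC is never expanded. But the sentences ruling out central review are unqualified, and Section 8 names no other reader for the endpoint.

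**Stronger readings a reader might infer.**
- That these conflicts would reverse the efficacy result. At an assumed one-sided 5% level the cut falls between 5 and 6 responders of 26, and at 2.5% between 6 and 7. But no level is stated, any single patient has this leverage at this size, and the documents do not say how many patients would be reclassified.
- That 12.5.8.7 makes hematologic improvement a further response category for DOR. Its second limb can be read as applying only where hematologic improvement was the response, and the trial's DOR is defined separately in 3.2 and 5.4.

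**Conclusion.** The point holds as a set of wording conflicts in current text. Applied as printed, 12.6.3 and 12.6.4 exclude AML patients with ANC ≥1 and platelets <100 from PR. They also leave those with <5% blasts and no transfusion independence outside CR, CRp and CRi. Whether a cytogenetic-only MDS response counts is undetermined, and two incompatible statements exist on who reads response.

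In size, the AML correction changes 6 of 16 profiles (3 each way) if 12.6.3 is a free-standing test, or 7 of 16 (all gains) if it lists exceptions to CR. This is a count of rule outcomes, not a frequency. It rests on the text as supplied, including a sign that needs checking against the source. A net bias in ORR in a known direction cannot be claimed: the direction depends on the reading for AML and on the intended list for MDS. ORR and the DOR population are affected; the DLT decision is not.

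**What to change.** 1. Check the source PDF, then correct the CRi platelet limit in 12.6.3 to <100 x 10^9/L, in line with 12.6.1 and 12.6.2.
2. State whether the CRi list is a requirement or a set of waivers, and word 12.6.4 so that recovered counts do not by themselves exclude a PR. If some incompleteness is required, give the category for <5% blasts with recovered counts but no transfusion independence.
3. Use one MDS responder list in 9.1.2, in 9.2.2.2 and for DOR, fixed before response data are analysed. Report cytogenetic-only responses separately, and repair the wording of 12.5.8.2.
4. Name one response reader for ORR and DOR and make 3.2, 12.6.6 and Section 8 agree. The 12.6.6 sentence on staying on study while progression is confirmed must also be reconciled with 6.2.2 and 8.1.2.6.9; no rule is proposed here.
5. In 3.2, replace the interval wording for ORR with the proportion in 9.2.2.2.

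The cost is protocol and SAP wording only. ORR and the DOR population may shift by one or a few patients.
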